This study was designed to have high power to test the primary hypothesis, that B4DT is non-inferior to gold standard CBT using a 4-point margin on the Y-BOCS. However, this study is not sufficiently powered to make confirmatory claims based on the results of the secondary analyses. This means that the results will be interpreted as explanatory (despite the fact that 95% confidence intervals of group differences will be reported to follow common practice in the field).

Methods

Study Design

We will conduct a single-blind (blinded outcome assessors), randomized (1:1), controlled non-inferiority trial comparing intensive 4-day CBT and gold-standard individual CBT for adults with OCD. The total number of participants will be 120 (60 per group). Participants will be assessed before treatment start, at week 4 and 7, 14 weeks after treatment start (primary end-point), and 7- and 16-months after treatment start (follow-ups). The Consolidated Standards of Reporting Trials (CONSORT) flow chart of the trial is shown in Figure 1. The study is pre-registered at XYZ (no. 123). Hypotheses were specified in advance. This process included determining outcome scales, statistical models and cut-offs, time-points of evaluation, and publishing analysis scripts before the beginning of data collection. During the trial, we will follow Good Clinical Practice (GCP) and all quality- and safety aspects will be regularly monitored by an external party, the Karolinska Trial Alliance (i.e. case by case monitoring of informed consent, inclusion/exclusion criteria, source data quality, and adverse events). The study has been approved by the Swedish Ethical Review Authority (EPM 2022-01713-01) and Helse Bergen HF (no. 490097).

CONSORT 2010 Flow Diagram

[figure not shown]

Figure 1. CONSORT-flow diagram. Abbreviations: B4DT, Bergen 4-day treatment; CBT, cognitive behavior therapy.

Participants

Patients referred to one of the two involved OCD specialist clinics in Stockholm and self-referred patients will be assessed for eligibility by a staff clinician during a full psychiatric assessment. Candidates that live within approximately one hour of both clinics and match the inclusion/exclusion criteria (see Table 1) will be offered participation in the study and asked to provide informed consent.

Table 1. Overview of inclusion and exclusion criteria

Inclusion criteria	≥ 18 years of age.
	Primary diagnosis of OCD according to DSM-5.
	Clinician-rated Y-BOCS score of ≥ 16

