	Written informed consent.
	To be willing and able to attend treatment at any one of the two treatment clinics, regardless of the clinic where the initial assessment took place (the two clinics are located at different locations in Stockholm, about 20 Km apart).
	Be fluent in Swedish.
Exclusion criteria	Other psychological treatment for OCD planned during trial period.
	Completed CBT with exposure and response prevention (ERP) for OCD in the last 12 months.
	Changes in psychotropic medication within the last 2 months.
	Bipolar disorder.
	Psychosis.
	Alcohol or substance dependence.
	Organic brain disorder.
	Hoarding disorder or OCD with primary hoarding symptoms.
	Suicidal ideation that would warrant close monitoring.

Abbreviations: CBT, cognitive behavior therapy; DSM-5, The Diagnostic and Statistical Manual of Mental Disorders, Fifth Edition; OCD, obsessive-compulsive disorder; Y-BOCS, Yale-Brown Obsessive-Compulsive Scale.

Randomization and concealment

A block randomization method will be applied where included participants are randomized to receive either B4DT (delivered at Ångestenheten, Psykiatri Nordväst), or gold standard CBT (delivered at OCD-programmet, Psykiatri Sydväst), regardless of their clinic of origin in blocks of 4 or 6. Block size will vary randomly. This approach was chosen to achieve balance in the allocation of participants to treatment arms and to prevent selection bias. It entails that patients assessed in one clinic may have to travel to the other clinic to receive treatment. A third party, the Karolinska Trial Alliance, will generate the randomization sequence. Participants will receive their randomization number based on order of inclusion.

Assessors will be blind to the study objectives as well as group assignment up to the last follow-up. To ensure that the blinding is maintained, assessors will be asked to guess the intervention received at each assessment after randomization, and to indicate whether the blinding has been broken (for example, the participant revealing details about the treatment). If blinding is broken, the participant will be assigned another assessor at subsequent follow-ups. The proportion of correct guesses will be estimated, and blinding is adequate if the proportion of correct guesses does not differ significantly from what would have been achieved by guessing treatment allocation by chance.

Interventions

Bergen 4-day treatment (B4DT)

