First, the clinics in this study are located in different parts of Stockholm. This means that some participants might prefer to be randomized to the clinic closest to their home, which could pose a risk of selection bias. In addition to highlighting the importance of only agreeing to participate if the location of both clinics are acceptable to the patient, we will continuously monitor the dropout rate in both arms and assess whether the distance to the clinic has caused dropouts. After data collection, we will evaluate the potential importance of travel distance on the risk of dropout and explore if and how this threatens the validity of the results.

Second, this study does not have sufficient statistical power to robustly assess the secondary outcomes. Hence, results from the secondary analyses will be interpreted as exploratory and need to be confirmed in independent datasets before firm conclusions can be drawn.

Last, blinding is always a problem in psychotherapy trials. In this study, while therapists and patients will be aware of which treatment arm they belong to, we aim to keep the outcome assessors, statisticians, and other investigators blinded. After each assessment, the outcome assessor will be asked to guess which treatment the participant has received and to indicate whether blinding has been broken. Sensitivity analyses will then be conducted to evaluate the potential effect of this type of blinding problem on the results.

Patient and public involvement

Patient representatives have not been involved in the design of the current study. The Swedish OCD Foundation (OCD-förbundet) supports the study by providing information about the project to their members and the public through their various channels. Results from the study will be reported to the public and relevant patient organizations (e.g., OCD-förbundet) through open access publishing and lectures.

Ethics and dissemination

Patient safety

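### Assessor blinding is declared adequate on a non-significant test against chance, so moderate unblinding would often be certified as adequate

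*Combined protocol and SAP*

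**What the plan says.** All references are to the combined protocol and SAP.

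- **Randomization and concealment.** After randomization, "assessors will be asked to guess the intervention received at each assessment after randomization", and assessors separately indicate whether blinding has been broken. If it has, a different assessor takes over at later follow-ups. The plan will estimate how often the guesses are right, and its criterion is that "blinding is adequate if the proportion of correct guesses does not differ significantly from what would have been achieved" under pure chance guessing.
- **Study Design.** Post-randomization assessments take place "at week 4 and 7, 14 weeks after treatment start (primary end-point), and 7- and 16-months after treatment start (follow-ups"), so each participant can contribute up to five guesses. Allocation is 1:1, which puts chance at 50%.
- **Limitations.** Patients and therapists know the arm, and assessors guess after each assessment. "Sensitivity analyses will then be conducted to evaluate the potential effect of this type of blinding problem on the results".

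The text gives no significance level, no highest acceptable proportion, no interval criterion and no analysis by arm. It does not say which visit is tested or how repeated guesses are combined.

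**The concern.** A non-significant result against 50% says only that the data did not rule out chance guessing. It does not show that accuracy was close to chance. The rule also rewards sparse data, because the fewer guesses collected, the easier it is to pass. The trial already respects this principle for its primary question, where similarity of the treatments must be shown against a pre-specified 4-point margin and not inferred from a non-significant difference.

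The verdict matters because the primary outcome is an assessor-rated Y-BOCS and the two treatment formats are very different, so a participant can easily give the arm away. Blinded rating is the main protection against expectation bias in that score. A report that follows the rule could state that blinding was adequate when the data do not support it.

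The rule also speaks of one proportion of correct guesses. If that proportion combines the arms, high accuracy in one arm can be offset by a guessing tendency in the other.

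**Working it through.** **Plan's own figures.** The plan gives no error rate for the blinding check, so there is none to reproduce. Its only related figure is the power of the primary analysis, stated as above 95% with 60 per arm and 10% missing. With 54 per arm, SD 4.07 and margin 4, SE = 4.07 × √(2/54) = 0.783 and power ≈ Φ(4/0.783 − 1.96) = 99.9%, which agrees. That power does not carry over to the blinding check.

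**Inputs from the documents.** Study Design: "The total number of participants will be 120 (60 per group"), allocated 1:1. Sample size calculation: 10% missing. Hence 120 × 0.9 = 108 guesses at one visit, 54 per arm.

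**Assumptions, not in the documents.** Week 14 is the visit tested, with one guess per participant; arms are combined (the natural reading, but not stated); the test is exact binomial against 0.50, two-sided 0.05. True accuracy is varied from 55% to 70%, because the plan does not say what would count as broken blinding.

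**Step 1: what passes.** With n = 108 the exact test does not reject for 44 to 64 correct; 64/108 = 59.3%. An approximate 95% interval around the highest passing result is 0.593 ± 1.96 × √(0.593 × 0.407/108) = 0.593 ± 0.093, or about 50% to 69%. A result labelled adequate can therefore be compatible with more than two-thirds correct.

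**Step 2: probability of a pass.** P(pass | p) = Σ (k = 44 to 64) C(108, k) pᵏ (1 − p)¹⁰⁸⁻ᵏ.

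| True proportion correct | n = 108 | n = 120 | n = 96 | n = 54 |
|---|---|---|---|---|
| 55% | 84% | 84% | 88% | 90% |
| 60% | 47% | 46% | 57% | 72% |
| 65% | 13% | 11% | 20% | 43% |
| 70% | 1% | 1% | 3% | 16% |

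The other columns use the same formula with their own acceptance regions (49–71, 38–58 and 20–34). At 60% and 65%, a pass becomes more likely at each step down from 120 to 54 guesses. The n = 54 column is also what applies if the test is done within one arm.

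**Step 3: combining arms.** With 54 guesses per arm, 90% correct in one arm and 30% in the other averages (90 + 30)/2 = 60%, and the sum of the two binomial counts falls in 44–64 with probability 47%. The overall figure cannot distinguish this from 60% in both arms.

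**Step 4: other reading of the visits.** If all five visits were combined, 5 × 108 = 540 guesses, with design effect 1 + (5 − 1) × ICC. Effective numbers are 540, 245, 180 and 129 for ICC 0, 0.3, 0.5 and 0.8. At a true 60%, the pass probability (normal approximation) is then 0.3%, 12%, 23% and 38%.

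**The case against.** The strongest reply is that the check works where it matters most. At 65% or 70% correct it fails blinding about 87% or 99% of the time. If one arm were 90% correct and the other at chance, it would pass only 0.5% of the time. That stands: gross unblinding would usually be found. A reader might infer that the rule certifies broken blinding about half the time. The documents do not support this as a general property. It holds only at about 60% true accuracy, with one guess per participant at a single visit and a two-sided 0.05 level, none of which the plan states.

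Second, pooling over arms is an inference, and pooling over visits would lower the pass rate (step 4). The analysis scripts in the online repository were not available and may settle both. This limits the numbers. It does not change the logic of the rule.

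Third, a 90%/30% split partly reflects a tendency to guess one arm and is not pure knowledge of allocation. That is fair, and only by-arm reporting can separate the two.

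Fourth, there are other safeguards. Assessors are blind to the study objectives, report broken blinding separately from their guess, and are replaced afterwards. The proportion of correct guesses will be estimated in any case, and the sensitivity analyses are not conditional on the adequacy test. These limit the consequence without repairing the rule. Replacement takes effect only at later follow-ups, so a rating unblinded at week 14 would remain in the primary analysis. The sensitivity analyses have no stated model or exclusion rule.

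Finally, a reader might infer that the rule inflates the false non-inferiority rate. Suppose 20% of B4DT ratings were unblinded and shifted by 1, 2 or 3 points in its favour. The bias would be 0.2, 0.4 or 0.6 points, and the error at the margin Φ(−1.96 + bias/0.783) = 4%, 7% or 12% instead of 2.5%. Those inputs are invented, and the bias would be the same under any blinding check. The non-inferiority decision rests only on the confidence bound against 4, so the rule does not cause this inflation.

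**Conclusion.** Wrong as written, and it should be changed. The plan does more than leave detail out: it states a decision rule that, followed exactly, can certify blinding the data do not support. On the single-visit assumptions above, the rule passes 84%, 47%, 13% and 1% of the time at a true 55%, 60%, 65% and 70% correct. The 60% figure ranges from 0.3% (five visits combined, independent guesses) to 72% (one visit, 54 guesses in one arm), depending on choices the plan leaves open.

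The harm is confined to an unsupported claim in the report that assessor blinding was adequate. The primary estimate, its confidence interval and the non-inferiority decision are not affected by the rule. The trial is also not open-label in the sense that would matter here: outcome assessors are meant to be blind, and the criticism concerns how that is verified.

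**What to change.** 1. In Randomization and concealment, delete the sentence that infers adequacy from non-significance. Instead, report the proportion of correct guesses (or a by-arm blinding index such as Bang's) with 95% confidence intervals, by arm and visit, with week 14 as the main visit. Draw no adequate/inadequate conclusion from a p-value. With 54 guesses in an arm, the interval near 50% is about ±1.96 × √(0.25/54) = ±13 percentage points, which shows the reader how much the data can say.

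2. In Limitations, and preferably also under the primary analysis, define the promised sensitivity analysis: the primary ANCOVA repeated without week-14 ratings flagged as unblinded, its upper confidence bound compared with 4, and reported whatever the guesses show. Label it supportive only, because dropping flagged ratings is a post-randomization exclusion that can itself bias the comparison.

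**Cost.** A few sentences and one extra model. The guesses and flags are already planned, so no new data are needed. The trial gives up a simple label of adequate blinding.

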Patients in this arm will receive an intensive treatment delivered mostly in group format, the Bergen 4-day treatment (B4DT) [6]. The group sizes will be 3-6 participants with a 1:1 patient to therapist ratio. In the week leading up to the intensive part of the treatment, participants will have two scheduled phone/video calls with a therapist to assess readiness and encourage participants to prepare relevant exposure tasks. Day 1 of the intensive treatment includes psychoeducation about the rationale for exposure with response prevention (ERP), and deciding on exposure tasks. Days 2 and 3 focus on individually tailored and therapist-assisted ERP in as many relevant settings as possible (up to 7 hours of ERP per day). In the evenings, patients should continue with self-guided ERP and may receive therapist support via text messages or phone calls on demand. In the afternoon of day 3, patients can invite relatives and friends to a psychoeducation session. Day 4 of the intensive treatment focuses on treatment summary and relapse prevention, as well as planning self-guided ERP for the upcoming 3 weeks. After 14 weeks, participants have individual follow-up sessions at the clinic where they summarize their experiences after completing treatment. There is no ERP during this session.

All groups will be led by a therapist with expertise in B4DT. All therapists will have participated in the Norwegian OCD-training program [12] or have documented equivalent training. Prior to participation, all therapists will have participated in at least two B4DT groups.

Individual CBT

Patients will receive 16 90-minute sessions of individual CBT for OCD with an emphasis on ERP, delivered over a time period of 14 weeks according to a validated protocol [10]. Sessions will be held twice weekly at a specialist clinic during the first 2 weeks and once a week for the remaining 12 weeks. Sessions 1-2 contain psychoeducation about OCD and CBT, goal setting, and planning of ERP exercises. Sessions 3-14 include therapist-guided ERP (at the clinic, in the patients' homes or elsewhere as needed) with planned self-practice ERP between sessions. Sessions 15-16 contain a summary of the treatment and lessons learned, as well as relapse prevention and planning of continued self-practice ERP.

Therapist competence and adherence

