The primary outcome measure is the blind assessor-rated Y-BOCS, which will be administered at pre-treatment, at weeks 4 and 7 during treatment, 14 weeks after treatment start (primary endpoint), and at the 7- and 16-month follow-ups [21]. Blinded assessors will undergo training prior to conducting clinician-rated assessment and practice on videos of OCD case examples. In order to be allowed to conduct assessments for the project, the assessors will have to deviate no more than 1 point on single items, no more than 2 points on the obsessions subscale and the compulsions subscale and no more than 4 points on the Y-BOCS total score compared to expert raters at the two clinics. Inter-rater reliability on the Y-BOCS will be reported.

Secondary clinician-administered outcome measures are the Clinical Global Impression – Severity and Improvement (CGI-S, CGI-I), the Patient Exposure/Response Prevention Adherence Scale (PEAS), the Structured Clinical Interview for DSM-5 for OCD and related disorders (SCID-5) and the Mini International Neuropsychiatric Interview. SCID-5 and MINI will be administered at pre-treatment to confirm the OCD-diagnosis and assess comorbidities

Secondary self-rated outcome measures are the Obsessive-Compulsive Inventory-Revised (OCI-R), self-rated Y-BOCS, Montgomery-Åsberg Depression Rating Scale—Self-Rated (MADRS-S), Work and Social Adjustment Scale (WSAS), Assessing Quality of Life 6 Dimensions (AQoL-6D) (for economic evaluation), Credibility/Expectancy Questionnaire (CEQ), Working Alliance Inventory—Short Form Revised (WAI-SR), the TIC-P resource use questionnaire (for economic evaluation), and the Negative Effects Questionnaire (NEQ). Participants will also rate their treatment preference measured on a 7-point Likert-type scale (pre-treatment and post-treatment).

Table 2. Assessments of secondary outcomes at different time points

	Pre-treatment	Week 4	Week 7	Week 15 (primary end-point)	7-month follow-up	16-month follow-up
Clinician-rated instruments						
SCID-5 (OCD)	X					
MINI	X					
Y-BOCS	X	X	X	X	X	X

CGI-S	X	X	X	X	X	X
CGI-I		X	X	X	X	X
PEAS*		X	X	x		
Self-rated instruments						
YBOCS-SR	X			X	X	X
OCI-R	X			X	X	X
MADRS-S	X			X	X	X
WSAS	X			X	X	X
AQoL-6D	X			X	X	X
TIC-P	X			X	X	X
NEQ				X	X	X
Other adverse events		X	X	X	X	X
CEQ**		X				
WAI-SR**		X				
Treatment preference	X			X		

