Abbreviations: AQoL-6D, Assessing Quality of Life 6 Dimensions; CEQ, Credibility/Expectancy Questionnaire; CGI-I, Clinical Global Impression–Improvement; CGI-S, Clinical Global Impression–Severity; MADRS-S; Montgomery–Åsberg Depression Rating Scale–Self-Rated; MINI, Mini International Neuropsychiatric Interview; NEQ, Negative Effects Questionnaire; OCI-R, Obsessive–Compulsive Inventory–Revised; PEAS, Patient Exposure/Response Prevention Adherence Scale; SCID-5, Structured Clinical Interview for DSM-5 Disorders; TIC-P, Treatment Inventory of Costs in Psychiatric Patients; WAI-SR, Working Alliance Inventory–Short Form Revised; WSAS, Work and Social Adjustment Scale; Y-BOCS, Yale–Brown Obsessive Compulsive Scale; Y-BOCS-SR, Yale–Brown Obsessive Compulsive Scale–Self-Rated; Other adverse events, semi-structured questions about potential severe adverse events and psychiatric care outside the study

* PEAS rated once at the last day of B4DT treatment

** CEQ and WAI-SR rated by participants at the last day of B4DT treatment and week 2 in individual CBT

Treatment-response will be defined as a $\geq 35\%$ reduction on the Y-BOCS and a Clinical Global Impression–Improvement (CGI-I) score of 1 ("very much improved") or 2 ("much improved"). Remission will be defined as a score of ≤ 12 on the Y-BOCS and a Clinical Global Impression–

Severity (CGI-S) rating of 1 ("normal, not at all ill") or 2 ("borderline mentally ill"). Recovery will be defined as a sustained remission status at the long-term follow-ups[8].

Safety and adverse events

Data on adverse events including suicidal ideation, and initiation of additional psychiatric care, will be collected at each assessment following inclusion, as well as through the regular contact between participants and therapists during treatment. A standardized self-rated questionnaire (Negative effects questionnaire, NEQ; [9]) containing 32 questions about incidents and negative effects will be used at the primary endpoint and follow-ups.

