Although there are no strict guidelines regarding the selection of non-inferiority margins, half the placebo-controlled effect of gold-standard treatment is often recommended as adequate [23]. The proposed non-inferiority margin of 4 is smaller than half of the 10-point effect for ERP on the Y-BOCS [4], and would therefore be a stringent non-inferiority margin. Moreover, a non-inferiority margin of 4 points gives similar precision compared to previous non-inferiority trials for OCD in adults that have used 5 points [19] or 3 points [20], and a previous non-inferiority trial in pediatric OCD that used a margin of 4 points [30]. From a clinical point of view, a 4-point margin on the Y-BOCS is considered a small but observable difference in OCD symptoms.

Secondary outcomes

While this study was designed to have high power to assess the primary hypothesis, we do not have sufficient power to robustly compare the secondary outcomes between the treatment arms without inflating the false positive rate. This means that the results from these analyses should be interpreted with caution. On secondary outcomes, our approach will be to compute 95% confidence intervals of group differences without comparing the bounds to any predefined margin. Because the non-inferiority testing procedure will not apply, the secondary outcomes will be analyzed using an intent to treat approach including all randomized participants.

Moreover, we do not plan to collect data continuously throughout the treatments since our focus is on the pre-post comparisons. This decreases the usefulness of statistical methods that make imputations based on past observations. Therefore, unless the proportion of missing data exceeds 10%, no data imputation methods will be used as default (unless stated otherwise). However, if the proportion of missing data exceeds 10%, we will perform maximum likelihood imputations based on demographics and the scores from the pre-treatment assessment to complement the complete case analyses. The implications of these analyses on the reliability of the results will be discussed.

Time to response

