(pretreatment) or the past 14 weeks (post-treatment and follow-up), and costs will be extrapolated to cover the entire period between assessments when needed. Costs from third party payer (including only intervention costs), healthcare, and societal perspectives will be analyzed in relation to clinical efficacy (responder status; cost-effectiveness analysis) and quality-adjusted life-years on the AQoL-6D (QALYs; cost utility analysis). Additional cost-effectiveness analyses will use remitter status as outcome. The economic analysis will be conducted using multiple imputation of missing values. Cost data and QALYs will be analyzed using generalized linear models (GLM) to allow for the consideration of other distributions and functional forms to fit the cost and outcome data [24]. Total costs will be analyzed while controlling for baseline costs. Total QALYs will be analyzed while controlling for baseline AQoL-6D utility values [25].

A micro costing framework will be used to estimate the cost of delivering the interventions prospectively. Intervention costs will include the therapists' time to deliver sessions, as well as any training needed. Healthcare resource use will be costed using national pricelists, and medication costs using market prices, and estimated by multiplying frequencies of resources used by unit costs. Unit costs for resources related to social support and assistance will be sourced from published sources or based on authors' own estimates. Productivity losses will be estimated using the human capital approach [26]. Productivity losses due to absenteeism from paid work will be the product of the number of days off from work by individuals due to mental illness by the average hourly salary rate in Sweden [27] including social fees. Losses due to absenteeism from unpaid work will be the product of the number of days not performing unpaid work by the estimated hourly cost of leisure time [28]. Productivity losses related to reduced efficiency at work will be estimated in the same fashion as productivity losses due to absenteeism, but additionally multiplied by a weighed score representing how the illness impacted the participants' productivity [29].

Additional outcomes used for quality assessment

Therapist competence and adherence

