Therapist competence will be scored using the Cognitive Therapist Scale-Revised (CTS-R) by independent raters not otherwise involved in the study. Descriptive information (average total score and standard deviation) for the two treatments will be presented.

Therapist adherence will also be presented using descriptive information (average adherence to protocol) as well as inter-rater reliability between independent assessors. For individual CBT, a session-by-session checklist of prescribed techniques will be used [5]. In B4DT, a checklist based on the content for each day in therapy, as well as adherence to B4DT-specific techniques, will be used.

Treatment preference, credibility and working alliance

Responses to the question about treatment preference will be presented descriptively at pre-treatment and the 4-month follow-up, respectively (means and standard deviations). In addition, an exploratory analysis will evaluate whether the degree of agreement between pre-treatment preference and treatment received moderates the main Y-BOCS outcome.

Treatment credibility and working alliance will be rated by participants at week 2 in treatment, and the total score means with standard deviations will be presented for both treatments.

Discussion

This study is the first trial to directly compare an intensive treatment for OCD, the Bergen 4-day treatment (B4DT) with traditional individual CBT delivered over 14 weeks. It will address the non-inferiority of B4DT, early rates of response for both treatments, as well as quality aspects including attrition and negative effects. By comparing the cost-effectiveness of both treatments, the study will be informative for decision makers in health care who strive for efficient use of resources. The study will also include follow-up until 16 months to evaluate the long-term effects of the treatments.

Limitations

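### Credibility and expectancy are rated at the end of B4DT but early in individual CBT, with no baseline rating, so the two arm means do not describe the same stage of treatment

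*Combined protocol and SAP*

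**What the plan says.** Three places in the combined protocol and SAP bear on when the Credibility/Expectancy Questionnaire (CEQ) and the Working Alliance Inventory (WAI-SR) are completed.

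- **Measurements, Table 2.** Each form has a single mark, in the Week 4 column, and none at pre-treatment. Both row labels carry a double asterisk.
- **Footnote to Table 2.** The double asterisk leads to: "CEQ and WAI-SR rated by participants at the last day of B4DT treatment and week 2 in individual CBT".
- **Statistical analysis, subsection on treatment preference, credibility and working alliance.** "Treatment credibility and working alliance will be rated by participants at week 2 in treatment". The sentence goes on: "the total score means with standard deviations will be presented for both treatments". The subsection stands under the heading "Additional outcomes used for quality assessment".

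The status of the two forms is mixed. The Measurements section includes both in the list that opens "Secondary self-rated outcome measures are". For secondary outcomes in general, the Statistical analysis section says that "our approach will be to compute 95% confidence intervals of group differences without comparing the bounds to any predefined margin".

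The Interventions section shows where the rationale ends and exposure begins. For B4DT: "Day 1 of the intensive treatment includes psychoeducation about the rationale for exposure with response prevention (ERP), and deciding on exposure tasks". Therapist-assisted exposure then fills days 2 and 3. For individual CBT: "Sessions 1-2 contain psychoeducation about OCD and CBT, goal setting, and planning of ERP exercises". Therapist-guided exposure starts at session 3.

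**The concern.** Participants and therapists know the allocation, as the Limitations section accepts. Credibility and expectancy ratings help a reader judge whether the arms entered treatment with similar expectations. To do that, the ratings should be taken at a similar stage, preferably before the active component has had time to work.

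Under the footnote they are not. The B4DT rating follows the whole exposure component. The CBT rating comes before most of it. The plan itself expects early benefit in B4DT: the Time to response section predicts faster relief there, and the Introduction cites response rates above 90%. A higher B4DT mean could reflect a more credible treatment, improvement already felt, or both. Without a baseline CEQ, the planned data cannot separate these.

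The analysis text adds a reporting risk. A reader who sees only that subsection could take the two means as collected at the same stage.

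**Working it through.** The plan states no figure for this point. The check compares the timing statements and counts the treatment received at each rating.

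**Inputs (Interventions section and Table 2 footnote)**
- B4DT: 4 days, exposure on days 2 and 3, up to 7 hours a day. Rated on day 4.
- CBT: 16 sessions of 90 minutes, two a week for 2 weeks, then one a week for 12 weeks. Exposure from session 3. Rated at week 2.

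**Check of the CBT schedule.** 2 × 2 + 12 × 1 = 16 sessions, which agrees with the stated total.

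**Dose at the rating**

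Sessions completed by the end of week w = 2 × min(w, 2) + max(0, w − 2).

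| | B4DT, day 4 | CBT, start of week 2 | CBT, end of week 2 |
|---|---|---|---|
| Share of course | about 100% of the intensive days | 2/16 = 12.5% | 4/16 = 25% |
| Exposure with a therapist | both exposure days | 0 sessions | 2 sessions (3 and 4) |
| Hours of that exposure | up to 2 × 7 = 14 | 0 | at most 2 × 1.5 = 3 |

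The B4DT share is given as about 100% because the footnote does not say when on day 4 the form is completed. The CBT range covers the whole of week 2 because the footnote does not name a session. The hours describe exposure to treatment. They do not measure bias.

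**The timing statements side by side**
- *Grid against footnote.* Table 2 has no column between pre-treatment and Week 4, so the mark sits in the first on-treatment column and the footnote gives the actual times. The column does not match the footnote, but it is not a separate schedule.
- *Footnote against analysis text.* They agree for CBT. For B4DT, agreement depends on when treatment starts, which the documents do not define. Counted from intensive day 1, day 4 falls in week 1. Counted from the preceding week with its two preparatory calls, day 4 could fall in week 2.
- *Effect of the second reading.* It reconciles the label only. The contrast of about 100% against 12.5% to 25% stays.

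**Use of the scores.** The only analysis named for CEQ and WAI-SR is means and standard deviations by arm. Neither enters a Y-BOCS model; the planned moderator analysis uses pre-treatment preference. Because both forms are also listed as secondary measures, the general rule on confidence intervals could be read to add an interval for the difference between arms.

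**The case against.** The best defence is that the footnote states the arm-specific times openly, so the choice may be deliberate. The scores are descriptive and filed under quality assessment. CEQ is not among the five secondary objectives. The primary outcome is rated by blinded assessors. No single moment is equivalent in two such different formats: before exposure, B4DT participants have had two calls and a day of group work, and CBT participants two 90-minute sessions. The documents do not give the CEQ items or say that the form must precede exposure. Labelling each mean with its rating time would remove much of the risk of misreading.

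Most of this stands, and it limits how far the point goes. Four stronger readings are tempting, and the documents do not support them:

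- *That the plan holds three rival schedules.* The Week 4 marks carry the footnote, so grid and footnote are one statement with a poorly placed mark.
- *That the analysis text asserts one common time for both arms.* Its reference to both treatments concerns the presentation of the means. A common time is implied by wording that does not separate the arms, but it is not stated.
- *That week 2 cannot exist in a four-day course.* It can, if the preparatory week counts as treatment.
- *That the ratings are contaminated by the trial outcome.* Both come well before the 14-week endpoint, and in B4DT three weeks of planned self-guided exposure still lie ahead. The supportable term is confounding with exposure and early response.

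The defence does not remove the unequal stages. Means printed side by side invite comparison even without a test. Pre-treatment preference does not replace CEQ, because which treatment a person would choose is a different question from how credible the assigned one seems. Labelling discloses the problem but does not give comparable ratings.

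**Conclusion.** The point holds as a minor weakness in the design of a supporting measure, together with wording that needs reconciling. Followed exactly, the plan yields a B4DT mean taken after essentially the whole intensive course and a CBT mean taken after an eighth to a quarter of the sessions, with no baseline rating. A difference between them cannot be read as a difference in credibility or expectancy alone.

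The size of any distortion cannot be computed. An upward shift in B4DT is plausible if participants who already feel better rate their treatment as more credible, but that is an assumption and the documents do not establish it.

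A reader might infer that the non-inferiority conclusion is at risk. It is not: CEQ plays no part in the primary Y-BOCS analysis, the error rate, the margin or the sample size. What is limited is the use of CEQ to judge whether expectations were balanced.

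**What to change.** 1. Give the CEQ in both arms after the rationale has been explained and before the first therapist-assisted exposure: at the end of day 1 in B4DT and at the end of session 2 in individual CBT. The stages will be closer, though not identical.
2. Reconcile the Table 2 marks, the footnote and the analysis subsection so that all three give the same arm-specific times.
3. Leave WAI-SR at the footnote's times if preferred. State those times in the analysis subsection, report the means as taken at different stages, and do not compare them directly.
4. If the CEQ cannot be moved, treat it in the same way as WAI-SR in step 3. This is the weaker option.

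The cost is small. One short self-rated form moves to an existing contact, with no new visit and no change to treatment. The downside is that the two forms are no longer handed out together. The change is best made before the first ratings, since an early expectancy rating cannot be recovered afterwards. The document is dated 31 October 2022, and inclusion was expected to start in November 2022.
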